QED PILOT TRIAL PROTOCOL

Redthread Youth Violence Intervention Programme evaluation

University of Birmingham

Principal investigators: [name],

[name] [name]

QED Pilot protocol template (includes a control group)

Evaluating institution: University of Birmingham

Principal investigators: [name], [name] [name]

Project title¹	Redthread Youth Violence Intervention Programme evaluation
Developer (Institution)	Redthread
Evaluator (Institution)	University of Birmingham
Principal investigator(s)	[name], [name] [name]
Evaluation plan author(s)/Co-investigators	[name], [name] [name], [name], [name], [name], [name], [name], [name].
Evaluation setting	Hospital / Community
Target group	10- to 17-year-olds presenting at hospital who are impacted by violence, exploitation or vulnerability. Redthread, NHS staff and other professionals at each recruitment site will also be interviewed.
Number of participants	In pilot phase all eligible participants across 4 proposed sites (Birmingham Queen Elizabeth hospital, Birmingham Children's hospital, St Mary's London and Queen Elizabeth

¹ Please make sure the title matches that in the header and that it is identified as a randomised trial as per the CONSORT requirements (CONSORT 1a).

	hospital, Woolwich) – approximately 350 CYP referred to Redthread and 150 engaged in a longer term programme.
--	---

Protocol version history

Version	Date	Reason for revision
1.5	18/8/22	YEF, RT and REC feedback
1.4	26/07/22	YEF, RT and REC feedback
1.3	13/7/22	YEF, RT and REC feedback
1.2	26/5/22	YEF feedback
1.1 [latest]	4/4/22	YEF feedback
1.0 [original]	16/12/2021	

Any changes to the design need to be discussed with the YEF Evaluation Manager (EM) and the developer team prior to any change(s) being finalised. Describe in the table above any agreed changes made to the evaluation design, research questions and approach, and the rationale for these.

Introduction

Background

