RT have commissioned a number of evaluations of its programme within different hospital sites. A non-peer reviewed published evaluation undertaken on the programme in St Mary's hospital in London by NPC associates^{18,26} showed promising findings, regarding reducing hospital re-attendance rates for violence (a statistically significant fall compared to a pre-programme control group). YP using the service and professionals referring into it were supportive of the programme. However, there were limitations in the study design which affected the ability to draw a causal conclusion. Similarly, an evaluation of the programme in the Queen's Medical Centre undertaken by research staff there²⁷ showed lower re-attendance rates for YP who participated in the programme (both short term crisis support and full programme of work), compared to those YP who were eligible for the programme but did not engage with it. These results were found for re-attendance for any reason and specifically for violence or assault.

Mechanism for action and key outcomes

During the co-design phase we worked with RT and their partners (Dartington Service Design Lab) to undertake a Theory of Change exercise. This work involved key stakeholders and is on-going but a draft has been produced and is described below. The work has helped clarify what the different components of the programme are and the likely channels which have outcomes for CYP. In turn, this has enabled us to clarify the short-, medium- and long-term outcomes that are expected. As a result, during our sessions, we have considered the outcomes at length in consultation with YEF and RT both separately and as part of a co-design phase. Following the co-design stage, it became clear that the primary outcome should be reattendance coded for a violence or abuse related reason to hospital within 12 months from their initial discharge date. These data are available for both intervention and controls (see detail later) and we are confident that there will be sufficient power to distinguish the two groups. The secondary outcome will be mortality by any cause one year post contact with RT (this will draw on NHS data captured in the Summary Hospital level Mortality Indicator and other data which captures mortality beyond 30 days post discharge).

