The matching is done by comparing the probability that an individual is assigned to the treatment group. Therefore, a matched pair comprises two individuals with the same probability of being assigned to the treatment group, yet one of them belongs to the control group. This probability is called the propensity score. The first step of PSM is to use logistic regression to calculate the propensity scores of each individual in the sample; the second step is to match these individuals according to their propensity scores. Once a propensity score has been calculated for each observation, we will ensure that there is overlap in the range of propensity scores across treatment and comparison groups by examining the scores graphically. A second check for the quality of matching is that, the propensity scores should have a similar distribution ("be balanced") in the treated and comparison groups. We will obtain an estimate of the propensity score's distribution by splitting the sample by quintiles of the propensity score. Because the number of individuals in the control group might be different than those in the treatment group, we will use kernel-based matching. We prefer the Epanechnikov kernel with a bandwidth of 0.06, which are common choices in the literature (see, e.g., Heckman, Ichimura and Todd, 1997).

We will ensure that there is a data sharing agreement between UoB and RT and UoB and the participating NHS trusts to support these activities.

Outcomes

For contextual information, following a co-design stage working with the intervention providers, it became clear that the primary outcome should be readmission (specifically violence/abuse related) to hospital at 12 months. These data are available for both intervention and controls and we are confident that there will be sufficient power to distinguish the two groups as well providing a comparable estimate with the published literature. The key secondary outcomes will be mortality by any cause one-year post contact with RT (this will draw on NHS data captured in the Summary Hospital level Mortality Indicator and other data which captures mortality beyond 30 days post discharge). We also plan to pilot the collection of the strengths and difficulty questionnaire (SDQ) and self-report delinquency scale (SRDS). However, the latter will be piloted in the opening phases of the study, as it is not likely we will be able to collect this data on control groups.

Control quantitative data

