For power calculations, acceptable levels of differences of outcome in the treatment group compared to the control group for the intervention to be considered a success would be established. Our considerations of sample size and minimally acceptable levels would also be informed by the existing literature in this area. A measure for this effect size is Cohen's d ,²¹ which takes positive values. Cohen suggested that $d = 0.2$ represents a 'small' effect size, 0.5 represents a 'medium' effect size and 0.8 a 'large' effect size. In the current study, we will aim to detect even 'small' effect sizes, i.e. where d takes values around 0.2 . Such effect sizes may be small, but they are meaningful in the current context and are standard in medical research, where sizes in the 0.05 to 0.2 range are frequently encountered. For $d=0.2$, with power of 80% , and assuming treatment and control groups of similar size, the minimum necessary sample is 392 individuals in each group, to a total of 784 . We will aim to use treatment and control samples of similar size. This is likely to be more feasible if constructing the control group from historic data, as there will be more suitable cases to draw on. If treatment and control groups are of unequal size, power calculations can be modified. Thus, the roughly 900 people who are engaged in a longer term programme over the 3 year course will give us adequate power provided the attrition rate is not much more than 50% . This is in line with previous studies conducted.

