As a result, we anticipate needing to recruit treatment and control samples from all 13 sites should the project run to a full trial. This will provide us with the maximal opportunity to meet the statistical power needed to assess our primary outcome (re admission). Additionally, where possible and statistical power is met, we will apply the principles of the Cochrane Progress Plus initiative²² to ensure the findings are reported in a manner applicable to the diverse population in these regions. Hence, during the first year pilot, we will not be able to make causal inferences as to the differences between the groups. However, one of the purposes of the first year is to ensure that data collection approaches are feasible.

Impact data analysis

We anticipate that gathering and analysing SDQ and SRDS measures, and NHS held data (regarding patient outcomes) would require NHS REC and HRA approval.

We will analyse the collected data in the following way. First, we will conduct a pre-treatment analysis, looking at summaries and descriptive statistics of the collected data. Our aim here will be to discover any systematic differences between the treatment and the control group. Second, we will apply propensity score matching to remove the systematic differences which may arise between these groups, due to biases related to the aforementioned observed characteristics. This method will create 'matching pairs' of 'similar' individuals. In each pair, one individual will have received the treatment, and one not. The average difference over all such pairs will constitute a reasonable estimate of the average treatment effect. We will test if this effect is statistically significant using statistical hypothesis testing (t-tests). Furthermore, we will examine if the detected differences are clinically significant, besides being statistically significant.

The pre-determined sample size (see earlier discussion of sampling considerations) needed to get what would be the agreed minimum effect should ensure that the study is sufficiently powered.

Appropriate guidelines will be followed for reporting an observational real world evidence trial:

<https://www.equator-network.org/reporting-guidelines/consort-spi/>

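### The protocol's single t-test rule, read by its general wording, also covers one-year mortality, where expected deaths are so few that the standard error behind the test is zero or too small

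*Protocol*

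**What the plan says.** The Impact data analysis section opens its method with "We will analyse the collected data in the following way". It then sets out a single sequence: describe the groups, match on the propensity score, average the differences between matched individuals, and test. The test is fixed: "We will test if this effect is statistically significant using statistical hypothesis testing (t-tests"). No other method is given for any outcome.

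Mortality is a between-group outcome. The section on mechanism and key outcomes states "The secondary outcome will be mortality by any cause one year post contact with RT", and the Outcomes section repeats it: "The key secondary outcomes will be mortality by any cause one-year post contact with RT". The data collection table lists mortality data for both the treated children and the controls. The two questionnaires (SDQ and SRDS) are planned for the treated group only, so mortality is the only named secondary outcome to which a treated-control test can apply.

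The population is "10- to 17-year-olds presenting at hospital who are impacted by violence, exploitation or vulnerability". The Sample size section says "the minimum necessary sample is 392 individuals in each group". The title table gives the pilot as "approximately 350 CYP referred to Redthread and 150 engaged in a longer term programme". The protocol states no expected death rate.

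**The concern.** A t-test on 0/1 data takes its standard error from the observed variance. A group with no deaths has an observed variance of zero, although the true uncertainty about its death rate is not zero. If neither group has a death, the statistic is 0/0 and there is no result. If only one group has deaths, the empty group adds nothing to the standard error, which is then too small.

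Reduced mortality is a long-term outcome in both the theory of change and the logic model. A report could therefore contain an unusable mortality test, or one in which very few deaths look more conclusive than they are.

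**Working it through.** **The plan's own figure.** Assuming a two-sided 5% level (the protocol states none), n per group = 2 × (1.960 + 0.842)² / 0.2² = 392.4. This agrees with the protocol's 392. The standardised effect behind it was chosen for readmission and says nothing about mortality.

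**Inputs.** 392 per group comes from the Sample size section. For the pilot, 150 treated comes from the title table, and a control group of equal size is assumed. The one-year death rate r is an assumption, shown over 0.1% to 1%.

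**Expected deaths per group, n × r.** At 392: 392 × 0.001 = 0.4 to 392 × 0.01 = 3.9. At 150: 0.15 to 1.5.

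**Chance of no deaths in either group, (1 - r)^(2n), with equal rates.**

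| r | 392 per group | 150 per group |
|---|---|---|
| 0.1% | 0.999^784 = 46% | 0.999^300 = 74% |
| 0.2% | 0.998^784 = 21% | 0.998^300 = 55% |
| 0.5% | 0.995^784 = 2% | 0.995^300 = 22% |

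**What the t-test's standard error implies.** The comparison is the 95% t-interval against the Newcombe interval (built from Wilson score limits), in percentage points, at 392 per group, with equal and unweighted groups.

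| Deaths | t-interval | Score interval | Width ratio |
|---|---|---|---|
| 0 v 0 | a single point at 0 | -0.97 to 0.97 | 0 |
| 1 v 0 | -0.25 to 0.76 | -0.74 to 1.43 | 46% |
| 2 v 0 | -0.20 to 1.22 | -0.53 to 1.84 | 60% |
| 3 v 0 | -0.10 to 1.63 | -0.33 to 2.23 | 68% |
| 4 v 0 | 0.02 to 2.02 | -0.13 to 2.59 | 73% |

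Worked line for 1 v 0: the difference is 1/392 = 0.255 points. The sample variance in the group with the death is 1/392, and in the other group it is 0. The standard error is therefore √((1/392)/392) = 1/392 = 0.255 points, and 0.255 ± 1.963 × 0.255 gives -0.25 to 0.76.

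**The 4 v 0 table.** The difference is 4/392 = 1.020 points and the standard error is 0.508 points, so t = 2.01 and p = 0.045 (pooled, Welch and paired agree). Fisher's exact test gives 2 × (392·391·390·389)/(784·783·782·781) = 0.124. Exact McNemar with four discordant pairs all in one direction gives 2 × 0.5⁴ = 0.125. Fisher needs 6 v 0 (p = 0.031), since 5 v 0 gives 0.062. At 150 per group, 4 v 0 gives about 0.045 against Fisher 0.122.

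**How often 4 v 0 arises with no effect (either direction, 392 per group).** 0.09% at r = 0.1%, 0.65% at 0.2%, 2.4% at 0.5% and 0.76% at 1%.

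**Overall error rate.** Enumerating all tables with equal true rates, the t-test rejects 0.1% of the time at r = 0.1%, 4.0% at 0.5% and 4.4% at 1% (392 per group). At 150 per group it rejects at most 2.9% over the same range.

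**Coverage when the true rates differ (392 per group).** The nominal 95% t-interval covers the true difference 74% of the time for 0.25% v 0.1%, 85% for 0.5% v 0.25%, and 94.5% for 1% v 0.5%. With equal rates it covers 95.6% or more for rates up to 1%, because the degenerate interval at zero happens to be right.

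**The case against.** The strongest reply is that the test holds its level, so a reader who infers an inflated false-positive rate goes too far. That is correct: the rate stays below 5% for equal groups. The fault lies in the standard error for particular small counts.

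Second, the protocol promises a test and not an interval. It does not say that a zero-width interval will be printed, and an analysis plan could define intervals properly. This also stands. The intervals above only show what the test's standard error implies. The test itself is nevertheless fixed in the protocol, and with no deaths it returns nothing.

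Third, the testing sentence does not name mortality, and the nearby discussion of power concerns readmission. Coverage of mortality is inferred from the general wording and from the absence of any other method. It is the natural reading but not an explicit statement.

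Fourth, this is a pilot protocol. It says that the first year will not support causal inference, and the timeline (recruitment from April 2022, final report in May 2023) leaves one-year mortality incomplete for most participants. The 392 per group belongs to the later efficacy study, which will have its own protocol. This reduces the immediate consequence. It does not remove the point, because the pilot report is still to contain a statistical comparison of the groups, pilot data may contribute to the final analyses, and sparse counts are more likely at pilot size.

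Fifth, the figures ignore matching and weights. The protocol describes matched pairs in one section and kernel matching in another, and weights would change the standard error. Unequal groups also change the result: 4/784 v 0/392 gives p = 0.157 with the pooled test and 0.045 with Welch. For the same reason, plain Fisher and Newcombe methods suit a crude count but not the matched effect estimate.

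**Conclusion.** The concern holds in a limited form. By its general wording the t-test rule reaches one-year mortality, and for that outcome it is a poor choice. With no deaths it is undefined, and with deaths in one group only its standard error is too small, giving an interval 46% as wide as a score interval at 1 v 0 and 73% at 4 v 0.

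A reader might infer that the plan is likely to produce false mortality findings. The documents do not support that: overall error is controlled, and with no effect the 4 v 0 table arises at most about 2.4% of the time at the rates examined.

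The sizes rest on an assumed one-year death rate of 0.1% to 1%, equal unweighted groups and a two-sided 5% level. The primary analysis is not affected. The correction is desirable but minor.

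**What to change.** In the Impact data analysis section, state that the t-test does not apply to mortality. For mortality, report the number of deaths and the denominator in each group, with an unadjusted exact or score interval for the difference. Label it descriptive and not adjusted for confounding, and say that a non-significant result is not evidence of no effect.

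If a test is wanted, choose one that fits the matching actually used: exact McNemar for 1:1 pairs. Otherwise state plainly that Fisher's test is applied to unmatched, unweighted groups.

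This takes a few lines of text and no extra data. The cost is wider intervals and giving up any confounding-adjusted claim about mortality, which these numbers could hardly support.

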Due to the complex and nationwide nature of the RT interventions we have ensured sufficient research fellow support. Their role will be critical to the success of the evaluation in terms of data collection, analysis, and routine monitoring of the project.

Risks

In order to manage risk and issues we will be using a risk register and maintaining an issues log. We have identified early risks and provided mitigation for these; these are included at the end of this document.

These include project-specific risks such as engagement with stakeholders, unavailability of data, and other risks such as unexpected unavailability of research staff.

We are particularly aware of risk related to Covid-19 and the team and the university has become familiar with secure online working. This includes online meetings, webinars and workshops and the team will have full access to the use of standard software such as Microsoft Teams and Zoom enabling business to be conducted smoothly if face to face meetings and workshops are not possible. All team members have regularly been using such software and are well versed in the functionality of it.

Additionally, given the increased possibility of illness or care duties, a resilient team has been created. Each work package in addition to a lead (or in this case co-leads), has a further senior researcher and research fellow associated with it. We also have a small cohort of experienced persons who have an advisory role (domain/methods experts) who can step in for a team member should there be an unexpected contingency that will make him/her unavailable. All the senior researchers supporting the overall project lead (project manager) have the ability and experience in this area to step in to become overall lead in case of anything unexpected happening that makes the project manager unable to carry on leading the project. Most of the personnel have not only led or co-led complex projects, they were involved in a recent work for the College of Policing to evaluate interventions as part of their vulnerability and violent crime programme and have a history of co-working minimising the risk of any difficulties of a multi-disciplinary team working together.

Our issues log will be used to collate key questions/issues and target the appropriate individual for a response which will be recorded in the log. Our risk register will identify, assess and control risks and uncertainties enabling us to improve the ability of the project to succeed. Our risk management technique, based on PRINCE2 principles, involves:

- Clear understanding of project context
- Establishing clear project objectives
- Regularly assessing and reporting risks
- Defining clear roles/responsibilities
- Establishing a support structure for risk management
- Monitoring for early warning indicators
- Establishing a review cycle, aiming for continual improvement.

Regarding ensuring the safety of the participants, none of the proposed activities for this research poses any risks to their safety beyond disease transmission though all and any government guidelines regards being Covid secure will be complied with. However, the researchers will keep this issue of safety under review during the course of the research and will take advice on the issue from RT staff. Particularly, during the interviews it will be important to note if participants (this includes not just CYP but all participants of our interviews) may be uncomfortable answering certain questions or being observed. In order to

minimise this, we will reassure participants that they are under no obligation to answer every or any question or discuss potentially distressing cases relating to difficulties in their personal life unless they are willing. Where participants feel particular distress, we will stop the interview and guide them to local counselling services which may assist them. We have developed distress protocols that we use routinely in our work and have adapted one specifically for this study. This is included at the end of this document. Also included is a link to Redthread's safeguarding policy.

Where fieldwork occurs in the RT offices, we will do this during hours when other personnel are present in the building to ensure that the environment is safe for the research team. We will also ensure that at least one staff in the building where we are interviewing are aware that we are interviewing. Further, we will create a WhatsApp group for immediate check in/check back after each interview between University staff. These arrangements are consistent with UoB's lone working guidelines (<https://intranet.birmingham.ac.uk/collaboration/ctl/Health-and-Safety/Lone-Working.aspx>, included below as an Appendix).

We believe this is a low to medium risk project and have identified (and mitigated for) a small number of potential early risks prior to project initiation. The issues log and risk register will be reviewed weekly by the research team. Any issues and/or risks will be shared at the earliest possible opportunity internally for mitigation and where necessary, if these are viewed as major risks, these will be escalated to 'named' project contacts within the Youth Endowment Fund.

Timeline

Dates	Activity	Staff responsible/ leading
Jan–Mar 2022	
Project set up – define referral pathways, record management processes
 
Evaluation set up – information sharing agreements, develop evaluation materials, gain ethics approval
	
RT: project team
 
UoB: PM/JSC

April 2022	
Project go live – recruitment of CYP into intervention, begin collecting case monitoring data
 
Begin collecting data
	
RT: project team and local teams
 
UoB: PM/JSC (lead) and UoB team.

April-December 2022	
Project operation
 
Gather quantitative data sources (outcome measures, case monitoring data, administrative data, control group)
 
Gather qualitative data (interviews with staff, referrers and CYP)
	
RT: project team and local teams
 
UoB: PM/JSC (lead) and UoB team.
 
UoB: EK (lead) and UoB team.

January 2023	Draft interim report	UoB team
March 2023	YEF make decision whether to progress to efficacy study	YEF
May 2023	Submit final report / support YEF publication process	UoB team

References

[figure not shown]
